#### 10. Describe the means of analyzing the data and evaluating the results.

- State the anticipated methods to be used for analysis and interpretation of the data.
- The methods must compliment the design of the study and the nature of the data which is being collected.

As a primary analysis of therapeutic benefit, we will use a paired t-test to compare the difference between baseline and final evaluation at the end of the home use period. A similar comparison using the Box and Block Test results will be used as the primary analysis of functional benefit. For these primary analyses, critical alpha will be adjusted using the Bonferroni correction to account for Type 1 error.

Secondary analyses will assess changes over time in each outcome measure as well as correlations between satisfaction and measures of motor impairment and function (both perceived and actual). We anticipate that the therapeutic measures will increase initially before plateauing while functional measures are expected to increase slowly at first with

continued gains across the home use period. We expect that satisfaction will be positively correlated with perceived improvements in function.

We will use single subject analysis to evaluate changes over time for each outcome measure. In order to capture individual effects, baseline to end of home use outcomes data will be plotted, with outcome measure score on the vertical axis and time/transition through conditions (therapy/training to home use) on the horizontal axis. Visual inspection in the form of change in trend (i.e., a systematic variation in the slope of the data points from one phase to the next) will be used. [name] has some experience with single subject analyses as detailed in a paper accepted for publication that evaluated ankle foot orthoses effect on community ambulation outcomes in children with cerebral palsy.

Spearman's correlation will be used to assess the relationship between OPUS satisfaction with device and Fugl-Meyer Assessment of Motor Recovery upper limb subsection score, as well as OPUS satisfaction with device and OPUS functional status.

As a primary analysis of MRI-based measures, we will use a paired comparison between baseline and post training evaluation (prior to home use period). For the TMS-based measures, we will compare data between baseline, at week 9, after the end of the therapy and after the end of the home-use phase. We will evaluate changes over time for each outcome measure.

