## 13. Please describe the research design and all study related procedures.

• Describe ALL PROCEDURES ASSOCIATED WITH THIS RESEARCH. This includes standard of care and research procedures.

• For complex studies please include diagrams and tables. Be sure to describe when each procedure will be performed. Be sure to provide information for each cohort, including normal controls).

The study requires 31 visits over 22 weeks and is divided into four parts: enrollment, orthotic fitting, therapy/training, and home use. See below table and description for details:

Part 1: Enrollment	Part 2: Orthotic Fitting		Part 3: Therapy/Training						Part 4: Home Use							Accessory to the second seconds			
Week 1	Weeks 2-3	Week S	Week 6	Week 7	Week 8	Week 9	Week 10	Week 11	Week 12	Week 13	Week 14	Week 15	Week 16	Week 17	Week 18	Week 19	Week 20	Week 21	Week 22
sment	íver ísíts)	2 x 1 hour sessions per week at LSCDVAMC Orthotic Assessment/Troi									Unsupervised at-home device use oubleshooting (as needed)								
Baseline Assessm	Cast, Fit, Del (minimum 3 v	1 x 2 hour Outcomes Assessment		1 x 2 hour Outcomes Assessment	X	1 x 3 hour Outcomes Assessment		1 x 2 hour Outcomes Assessment		1 x 4 hour Outcomes Assessment			1 x 2 hour Outcomes Assessment	X	X	1 x 2 hour Outcomes Assessment			1 x 3 hour Outcomes Assessment

Study Part 1 - Enrollment: The LSCDVAMC Institutional Review Board (IRB) requires consent both for screening and enrollment. Hence, after they provide screening consent, potential subjects will be screened to ensure that they meet the above criteria and are eligible to participate in the study. If eligibility criteria are met and the subjects provide enrollment consent, they will be enrolled in the study. The subjects will be evaluated and characterized at baseline and assessed at 2- or 3-week intervals for 18 weeks after orthosis delivery. Testing and outcome data collection will be done according to the schedule in Table 2 and in the section OUTCOME MEASURES

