Study Part 2 – Orthotic Fitting: Myomo will provide three MyoPro Motion-G devices to be used through-out the study and the fit of each device will be customized for each subject. These devices will be used on a rotating basis during the study period which means that at the end of the participation in the study, a subject will return the MyoPro-G device to PI. A Certified Orthotist from either the Cleveland VA or from Myomo will custom fit all orthoses individually to each subject for optimum performance. This process will require up to three visits to cast, trial fit and deliver the orthosis.

During the fitting process, first a plaster mold of the subject's arm will be taken. This mold is used for custom orthosis construction and fabrication typically takes 2 weeks. Once the orthosis has been constructed, the subject will be brought back for a fitting. During this fitting, the device will be calibrated to the subject's individual muscle signal profile and minor adjustments to the orthosis can be made to optimize comfort.

Subjects will receive both powered elbow and grasp at the same time. Throughout the duration of the study, the study orthotist will be available once a week to check the fit of the device and troubleshoot any device issues as needed.

The MyoPro is a relatively new, commercially-available custom fabricated upper limb orthosis that is individually fabricated for the patient over a positive model of the patient requiring education, training, and experience to custom-fabricate. It has been cleared by the Food and Drug Administration (FDA) for home use without direct supervision of a therapist [26]. The

MyoPro Motion G features include a lightweight elbow orthosis with a surface electromyography (sEMG) sensor, a lightweight hand orthosis with a sEMG sensor, a "motion W" manually set multi-articulating wrist and a rechargeable battery. MyoPro's sEMG controlled software continuously monitors and senses, but does not stimulate, the affected muscles. The system then filters and processes data, which is sent to a motor to enable the desired motion. The process is similar to the way power steering helps a driver maneuver a car. Based on the subject's abilities, the system parameters are adjusted by the therapist or orthotist. The power assist only applies an amount of force proportional to what users exert naturally; this encourages them to apply and maintain all the strength and control they have to achieve a range of motion.

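### Table 2 schedules the device-satisfaction survey (OPUS-Sat) at week 1, before the subject has the orthosis, so a satisfaction change or slope starting there cannot be interpreted; the satisfaction correlation also needs a visit and a level-or-change definition

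*Combined protocol and SAP*

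**What the plan says.** **Schedule.** Table 2 marks OPUS-UEFS, OPUS-Sat and CHART each at week 1 (baseline), week 13 and week 22, and Item 13 makes that table the schedule for outcome collection. The OPUS description under Aim 2 names the myoelectric arm orthosis as the thing rated. The OPUS-Sat items cover its weight, durability, ease of donning, skin irritation and pain in wear. The text introducing Aim 2 says, by contrast, that the patient-reported measures are added in the home-use period.

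**Device timing.** Fitting is Part 2, after enrollment and baseline. "This process will require up to three visits to cast, trial fit and deliver the orthosis", and "This mold is used for custom orthosis construction and fabrication typically takes 2 weeks". Subjects are then "assessed at 2- or 3-week intervals for 18 weeks after orthosis delivery".

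**Analysis (Item 10).** "Secondary analyses will assess changes over time in each outcome measure". In the single-subject analysis "baseline to end of home use outcomes data will be plotted", and the plots are judged by eye for "a systematic variation in the slope of the data points from one phase to the next". On satisfaction the plan states: "We expect that satisfaction will be positively correlated with perceived improvements in function". The named test is a Spearman correlation of OPUS satisfaction with the Fugl-Meyer score, "as well as OPUS satisfaction with device and OPUS functional status". No visit is given for either pair, and nothing says whether the values are levels or changes.

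**The concern.** A subject cannot say whether an orthosis is light, durable, easy to put on or painless before it has been made. A week-1 OPUS-Sat score is therefore missing, or a guess, or a rating of some other device. Item 10 would nevertheless carry it into the change-over-time analysis and use it as the first point of the plot. The apparent rise or fall from week 1 to week 13 would then describe how subjects coped with an unanswerable form, not what they thought of the device.

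The second part concerns the correlation. The stated expectation is about improvement, which is a change. If the Spearman analysis is run on levels, a positive result could arise because milder subjects are both more able and more satisfied. That would not show that satisfaction follows improvement.

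**Working it through.** **The plan's own figure.** The only computed figure is the sample size in Item 11. Exact noncentral-t power for a one-sided paired t-test at alpha 0.05 with d = 1.107 first reaches 0.95 at n = 11 (power 0.961), so the stated 11 reproduces. It rests on the Fugl-Meyer score and does not involve OPUS.

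**1. Where the OPUS-Sat marks fall.** The Table 2 columns are Screen, then weeks 1, 5, 7, 9, 11, 13, 16, 19 and 22. The OPUS-Sat marks sit in the 2nd, 7th and 10th columns: weeks 1, 13 and 22. As a check on the reading of the table, the TMS row counted the same way gives weeks 1, 9, 13 and 22. That agrees with the TMS time points in Item 10 (baseline, week 9, end of therapy, end of home use).

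**2. When the device arrives.**
- The Item 13 diagram places casting, fitting and delivery in weeks 2-3.
- The follow-up count gives 22 - 18 = about week 4.
- Casting in week 2 plus 2 weeks of fabrication gives 2 + 2 = about week 4.

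The week-1 rating thus precedes delivery by 3 - 1 = 2 to 4 - 1 = 3 weeks. On every route even casting comes after baseline.

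**3. What can be read.** Three ratings give two slopes: weeks 1-13 and weeks 13-22. The week-1 rating is 1 of 3 ratings and the origin of 1 of 2 slopes. Without it, two ratings and one slope remain. A change in slope between phases needs at least two slopes, so that reading is not available for OPUS-Sat.

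**4. Text against table.** Nine weeks of therapy from week 5 run to week 13, and nine weeks of home use run from week 14 to week 22. Week 22 fits the Aim 2 text, week 13 sits at the threshold of home use, and week 1 does not fit. OPUS-UEFS and CHART can be answered at week 1, so the conflict should be settled instrument by instrument.

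**5. Level against change.** Let B be baseline function, C its change, F = B + C the final level, and S satisfaction. Then cov(S, F) = cov(S, B) + cov(S, C). The left side can be positive with cov(S, C) = 0, and it can be diluted by B when cov(S, C) is positive. Ranks follow the same logic, though the identity is exact only for covariances.

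**6. Precision of a correlation at this size.** Take an observed Spearman value of 0.5 (my assumption, for illustration) and an approximate standard error on the Fisher scale of 1.03/√(n - 3); atanh(0.5) = 0.549.
- n = 20: 0.549 ± 1.96 × 0.250, which back-transforms to 0.06 to 0.78.
- n = 11: 0.549 ± 1.96 × 0.364, which back-transforms to -0.16 to 0.85.

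An interval will therefore say more than a p-value.

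**The case against.** **No test of satisfaction change is specified.** A reader might infer a planned baseline-to-end test of OPUS-Sat. The documents do not support that. OPUS-Sat is reached only through the general wording about each outcome measure, and the analysis is secondary, descriptive and largely visual. This stands, and it is why the point is minor. The general wording still makes no exception, so following the plan would use the week-1 value.

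**It may be only a schedule slip.** The Aim 2 text already gives a home-use timing. The three patient-reported rows are identical, and all carry the mark for assessment without the orthosis, which makes little sense for device satisfaction at any visit. The block may simply have been filled in uniformly. That is plausible, but Item 13 makes the table operative, so the slip would reach the data.

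**Some subjects may already wear an orthosis.** They could answer at week 1, but they would be rating a different device.

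**The correlation may have been meant as a change.** A reader might conclude that Item 10 uses the wrong method. The text does not go that far: it is silent on level or change, and the named correlations also serve the broader secondary aim of relating satisfaction to impairment and function. The sentence about perceived improvement is an anticipation, not a declared hypothesis. What stands is an incomplete specification.

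**A change score is not better in every respect.** It carries error from two visits, may share week-22 self-report error with satisfaction, and may have less power than the level. If milder subjects improve more, it also still carries some severity. All of this stands. The case for it is that it measures the quantity named in the expectation.

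**Conclusion.** The concern holds as a minor point on a secondary analysis. The week-1 OPUS-Sat rating falls about 2 to 3 weeks before delivery, contradicts the Aim 2 text, and cannot serve as a baseline for satisfaction with the study device. The week 13 to week 22 change remains usable. This rests only on the schedule, the device timing and the item content in the documents.

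The correlation point is narrower: the analysis as named cannot be matched to the stated expectation until the visit and the choice of level or change are given. How far a level correlation would mislead here cannot be sized, because the documents give no relation between satisfaction, baseline function and improvement.

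A reader might also infer that the whole week-1 patient-reported block is misplaced. It is not: OPUS-UEFS and CHART need a baseline. The Fugl-Meyer pair is not at issue, and neither the primary comparisons nor the sample size of 11 changes.

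**What to change.** 1. In Table 2, remove the OPUS-Sat mark at week 1 and keep OPUS-UEFS and CHART there.
2. Reconcile the Aim 2 text with the table, for example: OPUS-UEFS and CHART at weeks 1, 13 and 22; OPUS-Sat at weeks 13 and 22.
3. In Item 10, state that change in OPUS-Sat is assessed only from week 13 to week 22 and that OPUS-Sat is exempt from the change-in-slope reading.
4. In Item 10, add a Spearman correlation of week-22 OPUS-Sat with the week 1 to week 22 change in OPUS-UEFS, reported with a confidence interval. Keep the named level correlations, fixed at week 22, as descriptive.
5. State whether each OPUS-UEFS rating refers to function with or without the orthosis. Week 1 is necessarily without the study device, so otherwise the change may mix recovery with device assistance.

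The cost is one table cell and a few sentences. No new data are needed, and subjects complete one questionnaire fewer at baseline. The price is the noisier change score and its possible loss of power, which the retained level correlations partly offset.

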## 11. Provide a BRIEF DESCRIPTION of how the estimated number of study subjects needed for this research was determined

- If this is a quantitative study provide the method of determining sample size estimates.
- If multiple studies are planned provide a power analysis or justification for each one.

To determine our sample size, we utilized data obtained from a previous pilot study [26]. In that study of 9 patients with stroke, a change in the Fugl-Meyer Assessment of Motor Recovery upper limb subsection score of  $3.2 \pm 2.91$  was reported to be statistically significant [26]. This data was used to calculate effect size (d = 1.107) because we do not have pilot data for TBI. Using the G\*Power computer program [53] this effect size was used to estimate sample size. For a 1-tailed matched pairs t-test (comparing baseline to final evaluation at end of home use period) we would need a total sample size of 11 to detect an effect size of 1.107 with a critical alpha of 0.05 and power of 0.95. In order to account for possible attrition in subject numbers we will recruit 20 persons with TBI or stroke. Furthermore, we estimated that we would need to screen 70 subjects to recruit 20.

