# 40. Describe all procedures that minimize risks, please include study and standard of care procedures:

# Procedures that minimize Potential Foreseeable Risks-orthosis and study treatment/testing procedures

- The total duration of the study is about 31 visits over a period 22 weeks, which is a long commitment and increases risk of subject dropout. Subjects are informed of their time commitment during the screening phase and at enrollment consent and throughout their study participation.
- There is a possibility that some discomfort may arise while wearing the orthosis. Subjects will be required to wear the device for up to two hours during training and as long as tolerated at home. If at any time they feel uncomfortable, they are instructed to inform the researchers so that modifications can be made to the orthosis to improve comfort.
- There is a possibility that if the subject had ever experienced issues with shoulder instability or pain using the orthosis may cause these issues to flare up again Shoulder stability and pain will be monitored throughout the study to ensure that the device is not causing problems. Development of shoulder pain or additional subluxation during the course of the study would result in subject withdrawal from the study if modifications such as adding a shoulder harness were insufficient to overcome shoulder stability issues.
- The manufacturers of the orthosis have been careful to ensure that it is safe and cannot apply a dangerous amount of force to the arm or hand. Safety mechanisms have been implemented into the control software, the electronics hardware, and the mechanical hardware of the brace. For example, in the software commands that control the orthosis and the electronics of the orthosis, there are limits on the amount of force that can be commanded to the system. The mechanical system contains physical limits that prevent the orthosis from exerting force in an unsafe direction. In the worst case scenario, if all of these safety mechanisms fail, there is a small risk that the arm could be injured.

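### Item 11 sizes the study at an unadjusted one-tailed alpha of 0.05, but Item 10 will test the primary analyses at a Bonferroni-adjusted alpha; with two one-tailed tests, 11 completers give power 0.91 and 13 are needed for 0.95

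*Combined protocol and SAP*

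**What the plan says.** Item 10 (means of analyzing the data) sets out a paired t-test from baseline to the evaluation at the end of home use as the primary analysis of therapeutic benefit. It adds a second: "A similar comparison using the Box and Block Test results will be used as the primary analysis of functional benefit". It then commits to a multiplicity correction: "For these primary analyses, critical alpha will be adjusted using the Bonferroni correction to account for Type 1 error". It does not say how many tests are counted, whether they are one- or two-sided, or what the per-test level will be.

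Item 11 (number of subjects) takes its effect size from a pilot study of 9 stroke patients with a Fugl-Meyer upper limb change of 3.2 ± 2.91: "This data was used to calculate effect size (d = 1.107) because we do not have pilot data for TBI". The test is specified as follows: "For a 1-tailed matched pairs t-test (comparing baseline to final evaluation at end of home use period". The result is that the study would "need a total sample size of 11 to detect an effect size of 1.107 with a critical alpha of 0.05 and power of 0.95". Enrolment is then set higher: "In order to account for possible attrition in subject numbers we will recruit 20 persons with TBI or stroke". No dropout rate is given. Item 40 says of the schedule of 31 visits over 22 weeks that it is one "which is a long commitment and increases risk of subject dropout".

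**The concern.** The two items describe the same comparison at different significance levels. A Bonferroni correction over two or more tests puts each primary test below 0.05, yet the sample size was computed at 0.05. Nothing in the document suggests that 0.05 is already the corrected level; with two tests that would imply a familywise 0.10, which is stated nowhere.

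What is at stake is the meaning of the number 11. Item 11 presents it as the number of completers needed and treats the rest of the 20 as cover for attrition. A team watching retention against 11 would be working to a threshold that misses the stated power. Leaving the per-test level unstated also leaves the significance threshold open until the data are in hand.

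A related limit is that the calculation uses Fugl-Meyer pilot data only. The Box and Block Test has no effect size and no power statement in the document.

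**Working it through.** **Inputs**

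- d = 1.107, one-tailed paired t-test, alpha 0.05, target power 0.95 (Item 11).
- Two primary analyses, Bonferroni-adjusted (Item 10).
- 20 recruited (Item 11).
- Assumption A: two tests, one-tailed as in Item 11, so 0.05/2 = 0.025 one-tailed each.
- Assumption B: two tests, two-sided, 0.025 each.

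**Formula**

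For n completers the paired t statistic has n − 1 degrees of freedom and noncentrality d√n. One-tailed power is the probability that a noncentral t with these parameters exceeds the upper-alpha point of the central t. The two-sided version uses alpha/2 and adds the opposite tail. At n = 11 the noncentrality is 1.107 × √11 = 3.67.

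**Step 1: the plan's own figure.** At one-tailed 0.05, n = 10 gives 0.943 and n = 11 gives 0.961. N = 11 therefore reproduces, and it does so with no adjustment.

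**Step 2: the adjusted level**

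| Per-test level | Power at 11 | Smallest N for 0.95 | Power just below that N | Power at 20 |
|---|---|---|---|---|
| One-tailed 0.05 (as written) | 0.961 | 11 (0.961) | 0.943 at 10 | 0.999 |
| A: one-tailed 0.025 | 0.910 | 13 (0.955) | 0.936 at 12 | 0.997 |
| B: two-sided 0.025 | 0.830 | 15 (0.950) | 0.931 at 14 | 0.991 |
| Three one-tailed tests (0.0167) | 0.867 | 15 (0.964) | 0.949 at 14 | 0.994 |

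**Step 3: effect detectable with 11 completers at 0.95 power.** This is d = 1.068 at one-tailed 0.05, 1.210 under A and 1.351 under B. Multiplied by the SD of 2.91, these are 3.11, 3.52 and 3.93 Fugl-Meyer points. The planned d of 1.107 clears the first but not the other two.

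**Step 4: losses tolerated from 20 while keeping 0.95**

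- As written: 20 − 11 = 9 (45%).
- Under A: 20 − 13 = 7 (35%).
- Under B: 20 − 15 = 5 (25%).

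**Step 5: sensitivity to the rounding of d.** The printed pilot figures give 3.2/2.91 = 1.0997, not 1.107. An unrounded mean of 29/9 = 3.222 would explain the difference (3.222/2.91 = 1.107), but that mean is not printed. With d = 1.0997, N stays 11 at one-tailed 0.05 (0.959) and 13 under A (0.953; 0.907 at n = 11). Under B, n = 15 gives 0.947, so N becomes 16 (0.962) and the tolerated losses become 4 (20%).

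**The case against.** The strongest reply is that nothing in the design changes. Twenty will be recruited; if all finish, power is 0.997 under A and 0.991 under B. Even at exactly 11 completers, power under A is 0.91, and a 0.90 target would need just 11. Only the unusually high 0.95 target is missed. The arithmetic of Item 11 is itself correct, so this is an inconsistency between two items and not a miscalculation. All of that stands, and it is why the remedy is wording only.

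Secondly, 13 and 15 rest on choices that Item 10 leaves open. It does not name the Fugl-Meyer as the therapeutic primary measure; that is inferred from Item 11. It also uses the term primary for the MRI comparison, and Aim 1 lists several therapeutic measures, so more than two tests could be meant. This is fair, but every such reading lowers the per-test alpha further and leaves 11 completers below 0.95.

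Thirdly, the protocol never states a 45% loss allowance, and no expected dropout rate is given. That is correct: 9 of 20 is only what N = 11 and enrolment of 20 imply, and nothing shows that 35% or 25% would be exceeded.

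Finally, d from 9 patients is imprecise. Its 95% interval by the noncentral t runs from about 0.24 to 1.93, which dwarfs a shift from 0.961 to 0.910. This is true, but imprecision in d does not justify computing power at an alpha the analysis will not use.

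**Conclusion.** The point holds. The pairing of 11 completers with 0.95 power belongs to an unadjusted test that Item 10 says will not be used. For the Fugl-Meyer at the plan's own d, the power of 11 completers falls from 0.961 to 0.910 and the required number rises to 13, assuming two one-tailed tests. If the tests are two-sided, power falls to 0.830 and 15 are needed (16 if d is taken as 3.2/2.91).

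Confidence is high in the mismatch and in the direction of the effect. The exact replacement number depends on the number of tests and the sidedness, which the investigators must state. Enrolment of 20 is not shown to be inadequate; what shrinks is the attrition margin. No power statement can be made for the Box and Block Test from the documents. This should be corrected, but it does not threaten the study.

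**What to change.** - **Item 10:** add one sentence giving the number of primary tests in the Bonferroni correction, their sidedness and the per-test alpha. Name the Fugl-Meyer upper limb score as the therapeutic primary measure, if that is the intention.
- **Item 11:** restate the calculation at that alpha. For two one-tailed tests, suitable text is: *d = 1.107, one-tailed alpha 0.025 per test, 13 completers for 0.95 power (power 0.91 with 11).* For two-sided tests, state 15 completers, and confirm the unrounded d first because 15 only just reaches 0.95.
- **Attrition:** keep enrolment at 20 and say that this tolerates 7 losses (35%), or 5 (25%) if two-sided, at 0.95 power.
- **Scope:** say that the power statement covers the Fugl-Meyer test only.

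The cost is a few sentences in Items 10 and 11. No patients, visits or assessments are added; the only thing given up is the wider attrition margin implied by N = 11. The change should be made before the primary data are analysed, so that the significance threshold is fixed in advance.
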